4 STUDY DESIGN

4.1 OVERALL DESIGN

The proposed study is a Phase III trial powered to determine efficacy of two different doses of I-ACQUIRE for children 8 to 24 months old with PAIS and hemiparesis. The design is a prospective RCT in which 240 children will be randomly assigned to one of 3 treatment groups (N=80 per group): 1) Moderate Dose I-ACQUIRE (3 hrs/day, 5 day/wk X 4 wks), 2) High Dose I-ACQUIRE (6hrs/day, 5 days/wk X 4 wks), or 3) Usual and Customary Treatment (U&CT). I-ACQUIRE will be delivered by protocol-trained therapists and monitored weekly for dosage and treatment fidelity; U&CT will be provided by community therapists with dosage and approaches documented weekly. All primary and secondary efficacy outcomes rely on blinded assessments at baseline, end of treatment, and 6 mos post-treatment. Exploratory outcomes and supplemental clinical measures may provide valuable additional data about development and health in this sample of children with PAIS.

There will be a second phase of the I-ACQUIRE Study for the children who had been randomly assigned to Group 3 (Usual and Customary Treatment). Their parent(s) may choose to enroll (via a new IRB-approved consent process) to have their child randomly assigned to receive either the Moderate or High Dose I-ACQUIRE treatment. This will occur after the 6-mos Post-Treatment Assessment from the primary phase. Outcome data from this second or crossover phase of the study will not be used in the primary data analysis for this trial but will be available for exploratory and post hoc data analyses.

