described in detail in the ACQUIREc administration manual¹⁶ and training materials. We term this the MR3 Cycle (**m**ovement, **r**einforcement, **r**epetition, and **r**efinement).¹⁶ Activities are varied, game-like, and enjoyable for the infant; self-help activities provide frequent natural opportunities for the MR3 cycle.

4. Provision of therapy in natural settings. We provide therapy in natural environments, because this promotes generalization and maintenance of skills. For young children, this can include varied environments such as the home, childcare, or early intervention settings. Sometimes clinic settings can be set-up to be similar to home or childcare settings. Parents and family members often are present and join in some therapy activities.

5. Emphasis on total body and bimanual activities (as well as traditional arm/hand therapy activities)
Treatment activities extend to total body and gross motor activities that use the hemiparetic UE, e.g., sitting with stability, weight bearing, rolling, scooting, standing, crawling, and walking. Even with the cast, many gross motor bimanual activities can occur during treatment, e.g., crawling, rolling, carrying, pushing, or pulling large object).

6. Home Treatment Module developed as an active Parent-Therapist Partnership. We developed and use a parent-home training module (with supportive written materials and photo/videotapes). The therapist and parents meet at the beginning of treatment and at least weekly for 4 weeks. Initially, the therapist coaches the parent in the I-ACQUIRE processes, particularly concerning effective and ineffective use of operant conditioning. Parents help identify goals, introduce new activities, and help tailor therapy activities to promote the use of newly acquired skills in many different situations. Expectations are that parents enact their component for about 45 min per day on 5 of 7 days. (This can be divided into shorter times and include mother and/or father engagement. It is acceptable if only one parent provides the home program.) Daily review by therapists and parents of individualized home-based activities includes child responses and time spent and promotes two-way benefits for the child's treatment. Parents and therapists complete the Parent-Therapist Relationship Tool at the end of treatment week 4.

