6.4 STUDY INTERVENTION COMPLIANCE

We will define I-ACQUIRE treatment compliance as: (1) receiving therapy on at least 17 of the 20 intended days; (2) receiving the full daily dosage \pm 30 minutes on at least 15 treatment days; (3) wearing the cast continuously on at least 15 treatment days and over the weekends (NB: the cast is removed for the final 3 days of therapy intentionally to provide 3 sessions focused on bimanual activities); (4) the parent received training in the home-based component and provided evidence that this occurred on at least 12 days over the 4 wk treatment period; (5) completion of treatment occurs within 5 weeks of the first treatment session (this allows for a brief extension in the 4-wk treatment in the event of a short disruption, such as an illness, minor injury (not treatment-related), or family problem). We will examine the proportion of subjects in each I-ACQUIRE treatment group who did not receive this minimum level of treatment (i.e., met these criteria for treatment compliance) and seek to understand the likely reasons for non-compliance.

Whenever we restrict the analytic sample to the as-treated sample, we will report the number and characteristics of subjects who differ in treatment compliance (Moderate and High Dose I-ACQUIRE) or in distinct U&CT care subtypes (e.g. type of therapy, categorized treatment durations), and will consider if the final as-treated and Modified ITT samples differ in their sociodemographic or clinical characteristics. This is important so that study findings obtained from any as treated sample analyses can specify whether the results apply to the entire patient population or only to certain subgroups.

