8.3.3.2 RELATIONSHIP TO STUDY INTERVENTION

One of the most important components of AE reporting is determining the cause of the AE. It is imperative that the site investigator assess AE causality in terms of overall study participation and make an independent determination as to whether the AE was thought to be related to any study-related activity (i.e., study intervention, test article administration, study-related tests or procedures). For the subjects in U&CT, AEs that occur cannot be considered to be related to study participation, since the child previously was receiving this form of treatment (i.e., parents agree not to change the child's U&CT during the study period). Further, the study has no authority to obtain data from the child's community therapist(s) and thus cannot infer likely relationship to the U&CT intervention. For each Adverse Event, the relationship to the study treatment must be recorded as one of the choices on the following scale:

NOT RELATED (MUST HAVE 1)

- Unreasonable or incompatible temporal relationship to the intervention
- Event is clearly due to extraneous causes (e.g., underlying disease, environment)

-
- UNLIKELY (MUST HAVE 2)**
 - Reasonable or tenuous temporal relationship to intervention
 - Could readily have been produced by the subject’s clinical state, or environmental or other interventions
 - Does not follow known pattern of response to intervention
 - Does not reappear or worsen with reintroduction of intervention
-
- REASONABLE POSSIBILITY (MUST HAVE 2)**
 - Reasonable temporal relationship to intervention
 - Could not readily have been produced by the subject’s clinical state or environmental or other interventions
 - Follows a known pattern of response to intervention
-
- DEFINITELY (MUST HAVE 4)**
 - Reasonable temporal relationship to intervention
 - Could not readily have been produced by the subject’s clinical state or have been due to environmental or other interventions
 - Follows a known pattern of response to intervention
 - Disappears or decreases with reduction in dose or cessation of intervention and recurs with re-exposure

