9.4.2 ANALYSIS OF THE PRIMARY EFFICACY ENDPOINT(S)

The primary analysis (Aim 1) will use a modified intent-to-treat (mITT) study sample defined as those subjects who attend the baseline visit and continue to meet eligibility. This approach will permit exclusion of subjects who are randomized, but then drop out prior to any baseline data being collected, due to changes in eligibility or family circumstances that preclude any study participation. The sample size for analysis will be 240 subjects who meet the mITT definition.

Missing outcomes will be imputed as unfavorable, which is a conservative but reasonable approach given minimal (<5%) missing data. If the amount of missingness is unexpectedly high, e.g. >5%, then missing primary outcome data will be imputed via standard multiple imputation methods (i.e., via logistic regression model predicting outcome based on pertinent baseline and treatment data). The primary analysis will test the sequence of null hypotheses using fitted estimates from a logistic regression model, where the dependent variable is the dichotomized indicator of a favorable outcome, ≥ 7 new EBS skills above baseline at the end of 4-wk treatment and 6 mos post-treatment. An interim analysis for futility is planned after $N=120$ ($N=$ approximately 40/group) subjects complete the 6-month post-treatment visit using a non-binding O'Brien and Fleming type stopping boundary. Sensitivity analyses of the primary analysis will also consider the impact of distribution-based methods, using a generalized linear mixed-effects repeated measures model where change in EBS is modeled as continuous and the model is adjusted for baseline EBS score, treatment group, study visit (4 weeks or 6 months), and an interaction for treatment group and visit. Subgroup analyses will evaluate the impact of race/ethnicity, gender, neuroimaging biomarkers of injury, therapy fidelity, and parental involvement. The impact of U&CT dose variability will also be assessed in a model where the categorical indicator for treatment group will be replaced by a continuous covariate measuring total hours of therapy received and a categorical indicator for type of therapy.

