9.4.3 ANALYSIS OF THE SECONDARY ENDPOINT(S)

The secondary analysis (Aim 2) comparing changes in Mini-AHA among the three treatment groups will use a generalized linear mixed model with repeated measures to model the change in Mini-AHA at the End of Treatment and 6 mos. Post-Treatment; the same set of subgroup analyses are proposed for this endpoint. For the secondary analysis, the sequentially rejective hypothesis testing procedure must first reject the series of null hypotheses of no difference at 6 months post-treatment before testing for differences at 4 weeks post-treatment.

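### Therapy fidelity and parental involvement are listed as subgroup factors but arise after randomization: treatment comparisons by their levels lack randomized protection and, for fidelity against U&CT, are undefined

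*Protocol*

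**What the plan says.** For the primary endpoint, section 9.4.2 states: "Subgroup analyses will evaluate the impact of race/ethnicity, gender, neuroimaging biomarkers of injury, therapy fidelity, and parental involvement". For the Mini AHA, section 9.4.3 adds that "the same set of subgroup analyses are proposed for this endpoint". Neither section separates factors known before treatment from factors that emerge during it.

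Other sections show where the two factors come from.

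- **Fidelity.** Section 4.1 says "I-ACQUIRE will be delivered by protocol-trained therapists and monitored weekly for dosage and treatment fidelity". For the control arm it says "U&CT will be provided by community therapists with dosage and approaches documented weekly", with no mention of fidelity.
- **Parental involvement.** The home module is one of the core components of both I-ACQUIRE doses (6.1.1): "Expectations are that parents enact their component for about 45 min per day on 5 of 7 days". Section 6.4 makes it a criterion of I-ACQUIRE compliance: "the parent received training in the home-based component and provided evidence that this occurred on at least 12 days over the 4 wk treatment period". Section 6.1.1 also says "Parents and therapists complete the Parent-Therapist Relationship Tool at the end of treatment week 4".
- **Before randomization.** The only parental item is willingness to take part in the home component, which section 5.1 requires of every family.

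**The concern.** A subgroup analysis of a randomized trial keeps its validity because the factor is settled before treatment can influence it. Each level then contains its own small randomized comparison. A factor that emerges during treatment does not have this property. Children whose therapy ran with high fidelity, or whose parents kept up the home program, may differ in health, tolerance of therapy, family circumstances or early response from those for whom this did not happen. The protocol itself suggests such routes. Therapists may change or stop activities when an infant is distressed (6.1.1), illness and family problems can interrupt sessions (6.4, 7.1), and families and therapists know the assignment (6.3).

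At stake is how a result would be read. A finding that the therapy works only with engaged parents, reported beside results by gender or MRI biomarker, would look like a randomized subgroup finding. Section 2.3.3 expects the trial to inform treatment recommendations and insurance coverage.

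**Working it through.** The protocol gives no figure for these analyses, so there is nothing of its own to reproduce. The main check is a comparison of the text; the arithmetic only illustrates possible size.

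**Step 1: timing and availability by arm**

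| Factor | When it is known | Described in U&CT? |
|---|---|---|
| Race/ethnicity, gender | Before treatment | Yes |
| Neuroimaging biomarkers | Clinical MRI supplied as a condition of entry (5.1) | Yes |
| Therapy fidelity | Weekly during I-ACQUIRE (4.1) | No; dosage and approaches only |
| Parental involvement | Over the 4-week treatment period (6.4) and at the end of week 4 (6.1.1) | No; the home program is part of I-ACQUIRE |

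Two of the five factors fail on timing. Willingness (5.1) cannot stand in for involvement, because every enrolled family has it.

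**Step 2: which contrasts remain**

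- *I-ACQUIRE against U&CT within a fidelity level:* undefined, because no U&CT child has a described value.
- *I-ACQUIRE against U&CT within an involvement level:* no U&CT counterpart is described. If one were recorded, it would still arise after assignment.
- *High against Moderate Dose within a level:* computable, but both factors may depend on the assigned dose, so the groups within a level need not be comparable.

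**Step 3: possible size if a selected I-ACQUIRE subset is compared with U&CT**

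Section 9.2 expects up to 15% success in U&CT. Everything else here is an assumption:

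- no treatment effect, and 15% success in both arms;
- a standard normal prognosis U with logit(success) = a + bU, where b is 0.5 or 1.0 and a is set to give 15% overall;
- in the I-ACQUIRE arm, a latent factor ρU + √(1 − ρ²)·e, where e is independent standard normal noise, split at its median;
- in the control arm, a factor unrelated to U;
- 2,000,000 children per scenario, half per arm.

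Differences from control are in percentage points, taken before rounding.

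| b | ρ | I-ACQUIRE success, high / low | Difference, high level | Difference, low level | False gap (high − low) |
|---|---|---|---|---|---|
| 0.5 | 0 | 15.0% / 15.0% | +0.1 | 0.0 | 0.1 |
| 0.5 | 0.3 | 16.5% / 13.4% | +1.6 | −1.6 | 3.2 |
| 0.5 | 0.5 | 17.4% / 12.5% | +2.5 | −2.5 | 5.0 |
| 1.0 | 0 | 15.0% / 15.0% | 0.0 | 0.0 | 0.0 |
| 1.0 | 0.3 | 17.7% / 12.3% | +2.7 | −2.7 | 5.4 |
| 1.0 | 0.5 | 19.5% / 10.5% | +4.5 | −4.4 | 8.9 |

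The overall difference between arms stays within 0.1 point of zero throughout.

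*Hand check for b = 0.5.* The shift per level is about b × p(1 − p) × ρ × √(2/π). With ρ = 0.3 this is 0.5 × 0.15 × 0.85 × 0.3 × 0.798 = 0.015. With ρ = 0.5 it is 0.025. Both are close to the simulated values.

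**The case against.** The strongest reply is that section 9.4.2 does not spell out the faulty contrast. It commits to evaluating the impact of five factors and gives no interaction model and no comparison of a selected I-ACQUIRE subset with all of U&CT. Model detail may lie in a statistical analysis plan that is not shown. For fidelity in particular, comparing levels within the I-ACQUIRE arms is a possible reading. This stands in part: the protocol does not state a wrong formula. But it puts the two factors in one undifferentiated list with race/ethnicity, gender and MRI biomarkers, for an endpoint analyzed across three arms, and nothing there limits them to an association within I-ACQUIRE.

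A second reply is that the issue is handled elsewhere. Section 9.1 already names family engagement as a predictor in exploratory sensitivity analyses of repeated EBS scores, and section 6.4 promises to describe children who differ in compliance. Both are sound, but section 6.4 speaks of as-treated samples, and neither section alters the subgroup list.

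Third, earlier studies in section 2.2 report high fidelity and full dosing. If that repeats, there may be little variation to split on. That would limit the damage, and also the usefulness of the subgroups.

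A reader might infer that these subgroup effects are certain to be biased. The text does not support that: bias requires the factor to track prognosis or response, and the protocol gives no figure for this. A reader might also assume 25% success in highly involved and 5% in less involved families, half of each, and read off a 20-point false difference. With the average at 0.5 × 25% + 0.5 × 5% = 15%, that gap is +10 − (−10) = 20 points, which only restates the assumption.

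**Conclusion.** The point holds as a moderate flaw in the subgroup list. Therapy fidelity and parental involvement arise after randomization and are tied to I-ACQUIRE delivery, so treatment comparisons within their levels are not randomized comparisons and may be biased. For fidelity, a within-level contrast with U&CT is undefined as the protocol stands.

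The size of any bias cannot be taken from the document. In the illustration it runs from nil at zero correlation to a false high-versus-low gap of about 3 to 9 points at correlations of 0.3 to 0.5, and more under stronger assumptions. This rests on a factor that tracks prognosis in the I-ACQUIRE arm but not among the control children it is compared with. The case for changing the list does not depend on the figure.

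Two further inferences go too far. One is that the main result is at risk: the primary analysis compares mITT groups as assigned, and the testing sequence in section 9.4.1 names no subgroup. The other is that leaving age off the list is an error: section 4.2 says only that plasticity may relate to age, so adding it is optional.

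**What to change.** In sections 9.4.2 and 9.4.3, limit treatment-by-subgroup analyses to factors fixed before treatment: race/ethnicity, gender and neuroimaging biomarkers. Age may be added, since section 4.2 names it as a possible modifier.

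Move therapy fidelity and parental involvement to an exploratory association analysis within the two I-ACQUIRE arms, adjusted for assigned dose, baseline EBS and age. Label it non-randomized and align it with the exploratory use of family engagement in section 9.1.

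The cost is wording only. No new data are needed and no sample-size figure changes. What is given up is any statement about I-ACQUIRE against U&CT by level of fidelity or involvement, which the described data could not support as a randomized comparison.

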Cross-study comparison of changes on the Emerging Behaviors Scale in Figure 1. EBS outcomes combined across studies show statistically significant mean EBS gains of 9.9 new UE skills. For Study 1A, the mean EBS gain of 9.3 skills for treated subjects was >4 times the U&CT mean gain of 2.3 new skills. After the U&CT subjects received ACQUIREc, their EBS scores showed a gain of 8.4 skills.

What comprises U&CT? In our studies, all patients were receiving U&CT when enrolled. The

Figure 1: Emerging Behaviors Scale (EBS): Mean Gain Scores across Studies of ACQUIRE

[figure not shown]

mean U&CT dosage has been fairly stable for 2 decades – about 2.2 hrs/wk (range of 1 to 3 hrs/wk) of OT/PT. The U&CT content was remarkably similar across patients, often described as an individualized therapy that combines motor learning, sensory integration therapy, neurodevelopmental therapy (NDT), and play techniques. More recently, up to 25% of the patients enrolled in our ongoing RCTs had some form of modified CIMT previously; this seldom met minimal criteria to qualify as evidence-based CIMT – that is, having the 3 CIMT core elements of i) high dosage (>2 hrs/day for at least 10 days within 2 wks), ii) active shaping and repetitive practice of UE skills, and iii) use of constraint. Examples of non-evidence-based or insufficient forms of CIMT are: 1 hr of therapy/wk with constraint and parent practice of 15 – 30 min/ day; 2 90-min sessions/wk for 6 wks using a hand mitt; and parents applying their own constraint. For this revised application, we asked clinical sites about the forms and dosages of typical U&CT: mostly, infants receive one or two 60-min sessions of OT and/or PT/wk in a community or hospital clinic or during a home visit. The U&CT therapy is described as a combination of techniques and the goals are individualized. Almost never is the content or therapeutic approach documented in detail. Many also receive speech therapy. Thus, the range in U&CT is relatively modest in dosage and content (therapy approach) with the caveat that some sites provide “modified CIMT.”

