9.3 POPULATIONS FOR ANALYSES

Modified Intent to Treat (mITT) Sample

All efficacy analyses (primary, secondary, and exploratory) will be conducted using a modified ITT (mITT) sample. That is, the evaluable sample includes all randomized subjects who continue to meet the inclusion/exclusion criteria at the time of Baseline Assessment and who complete the Baseline Assessments prior to treatment initiation, notwithstanding whether or not the subjects completed the study treatment protocol for their group. A sensitivity analysis will consider differences between the mITT sample and a traditional ITT sample, which is inclusive of the mITT sample but also analyzes all subjects who are randomized but withdraw, are lost to follow-up, or no longer meet inclusion criteria prior to the time when a baseline assessment would have occurred.

As Treated Sample.

Sensitivity analyses will use the as treated sample when specified. That is, the evaluable sample includes all randomized subjects, regardless of whether or not the subjects completed the treatment as planned. In contrast to the mITT sample which categorizes treatment by randomly assigned group, the As Treated Sample analyses will consider the dose of treatment defined as the actual number of treatment sessions as well as total hours received (e.g., a child who is perfectly compliant in the Moderate Dose or High Dose I-ACQUIRE is expected to get 60 or and 120 hours of I-ACQUIRE treatment respectively).

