Between Day 17 and Day 20 of I-ACQUIRE treatment.	
Stop Tx. At this particular time, the child will have qualified for receiving what was a priori defined as a sufficiently “full dose” of the treatment. However, we realize that Days 17 – 20 are distinctive because: i) we remove the cast; ii) we concentrate our focus on promoting bilateral activities – during formal therapy session and during parent-enacted home treatment; and iii) at the end, parents and the therapist finalize a post-treatment plan. For children and families who have their study participation disrupted at this timepoint, we propose working distally with the parents to provide bilateral shaping and activities and to develop the Post-treatment plan. We propose documenting these in the Web-DCU system using the Daily Log format we already have. The child and family will not require a new complete (or partial) treatment. IMPACT: #1. Additional time will be needed for the I-ACQUIRE Study central team at the Virginia Tech Treatment Implementation

	center to develop individualized and online modules for Days 17 – 20. #2. The post-treatment assessment 1 likely will not be conducted. (See below for how this will be handled.)
During Usual and Customary treatment (UCT), from start to end of the 4 week period	
For children in the UCT group, the local study coordinator or a team member needs to be in contact with a family to determine if there are disruptions in the child's receipt of usual therapy.
 
Note: we will not be advising parents about whether to continue or to stop the UCT that they arrange and for which they are responsible. Any disruption to the child's UCT will result in the need to re-schedule when the trial resumes. As above, this will necessitate scheduling a new pre-treatment (baseline) assessment as well as the treatment month. The child can be > 24 months old when re-scheduled, up to 36 months old.). Finally, it is likely a disrupted UCT period will be associated with a disruption to the Post-treatment Assessment 1 (see below).

At Post-treatment Assessment 1	STOP. This can be re-scheduled when the trial resumes. IMPACT: At this time, we are recommending allowing a protocol deviation for this to extend to 3.49 months after treatment ends (rather than the current recommendation of 2 weeks). We may need to re-consider this proposed endpoint for this assessment depending on duration of study suspension.

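### The model meant to assess U&CT dose variability fits one common hours slope that is set mainly by the I-ACQUIRE dose contrast, so it does not estimate the effect of U&CT dose

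*Protocol*

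**What the plan says.** Protocol 9.4.2 specifies a logistic model for the primary outcome, with sensitivity and subgroup analyses. It closes with a further model: "The impact of U&CT dose variability will also be assessed in a model" in which the group indicator is "replaced by a continuous covariate measuring total hours of therapy received and a categorical indicator for type of therapy". The sentence mentions neither an hours-by-type term nor a fit restricted to the U&CT arm, and it does not say over what period hours are totalled.

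The doses are given elsewhere:
- **I-ACQUIRE.** Section 9.3 says that a fully compliant child "is expected to get 60 or and 120 hours of I-ACQUIRE treatment respectively".
- **U&CT.** Section 2.2 puts the dose in the sponsor's earlier studies at "about 2.2 hrs/wk (range of 1 to 3 hrs/wk) of OT/PT" and says that "the range in U&CT is relatively modest in dosage and content (therapy approach", with a caveat about sites that offer modified CIMT.
- **Window.** The COVID-19 addendum (11.1) treats U&CT as having a treatment month: "During Usual and Customary treatment (UCT), from start to end of the 4 week period".
- **Allocation.** Section 4.1 has children "randomly assigned to one of 3 treatment groups (N=80 per group", and says that U&CT dosage and approach are documented weekly.

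**The concern.** The question is whether outcomes depend on how much U&CT a child receives. It matters because 9.2 allows for up to 15% of U&CT children meeting the primary criterion, on the ground that some may now be getting more effective therapy than in the past. If control outcomes rise with U&CT hours, the I-ACQUIRE advantage would be smaller where U&CT is heavier.

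A model with one hours slope for all children cannot show this when nearly all the spread in hours lies between the two I-ACQUIRE doses. Its slope restates High v Moderate. It would be positive and usually significant even if U&CT hours had no effect, and nearly the same if they had a strong effect in either direction.

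**Working it through.** **Inputs**
- I-ACQUIRE hours: 3 x 5 x 4 = 60 and 6 x 5 x 4 = 120, which reproduces the figures in 9.3.
- U&CT hours: 1 to 3 a week over 4 weeks = 4 to 12. A uniform spread is assumed.
- 80 children per arm (4.1).
- Favourable rates of 15%, 40% and 70% for U&CT, Moderate and High (9.2).

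The protocol gives no figure for this model, so there is nothing further of its own to reproduce.

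**1. Where the variation in hours lies (4 weeks, type separating I-ACQUIRE from U&CT)**
- Within I-ACQUIRE: 160 x 30² = 144,000.
- Within U&CT: 80 x 8²/12 = 427.
- 60 v 120 share: 144,000 / 144,427 = 99.7%.

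With U&CT at its most extreme (half at 4 h, half at 12 h), the U&CT sum of squares is 80 x 4² = 1,280, a share of 0.9%.

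**2. The same with logistic weights p(1-p)** (0.24 Moderate, 0.21 High, 0.1275 U&CT)
- I-ACQUIRE information: 80 x (0.24 x 0.21 / 0.45) x 60² = 32,256.
- U&CT information: 80 x 0.1275 x 64/12 = 54.4.
- 60 v 120 share: 32,256 / 32,310 = 99.8%. SE of the common slope: 1/√32,310 = 0.0056.

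**3. What the slope estimates.** The planned 40% v 70% alone gives [ln(0.7/0.3) - ln(0.4/0.6)] / 60 = 1.253/60 = 0.0209 per hour. I then fitted the stated model to expected data, varying the true U&CT slope with the mean U&CT rate held at 15%:

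| True U&CT slope per hour | U&CT rate at 4 h and 12 h | Fitted slope, type separates | Fitted slope, type does not separate |
|---|---|---|---|
| -0.4 | 40%, 3% | 0.0203 | 0.0225 |
| 0 | 15%, 15% | 0.0208 | 0.0228 |
| +0.4 | 3%, 40% | 0.0214 | 0.0230 |

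The SE is about 0.0056 in the third column and 0.0034 in the fourth. With type separating, the hours term was significant in 97% to 98% of 1,500 simulated trials in each row, including the row where U&CT hours have no effect. In the fourth column the slope is a three-arm contrast (about 8 v 60 v 120 h) and is just as insensitive.

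**4. A longer window.** Suppose hours run for about 30 weeks (an assumption), so that U&CT spans 30 to 90 h.
- If only the U&CT arm's U&CT hours count, the U&CT sum of squares is 80 x 60²/12 = 24,000 and the 60 v 120 share is 144,000/168,000 = 86% (91% with logistic weights).
- If every child also accrues U&CT hours, variation within the I-ACQUIRE arms adds 160 x 300 = 48,000. The share is 144,000/216,000 = 67% (70% weighted).
- In the first of these cases, true U&CT slopes of -0.05, 0 and +0.05 give fitted slopes of 0.015, 0.019 and 0.023. The slope moves, but it is a blend. It is positive when the true U&CT slope is negative, and about 3.6 SEs from zero when that slope is nil.

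**5. What a U&CT-specific slope could show (4 weeks).** Fitting hours within U&CT, or adding an hours-by-type interaction, returns the true slope in each row of the table. The SE is 1/√54.4 = 0.136 at a zero slope and about 0.165 at ±0.4, with 80 x 0.15 = 12 favourable outcomes expected. The smallest slope detectable with 80% power is 2.80 x 0.136 = 0.38 per hour, an odds ratio of about 21 between 4 and 12 h.

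**The case against.** The target is one sentence on an additional analysis. It names two covariates and leaves the counting window, the coding of type and any interaction unstated, all of which a SAP could settle. Section 6.4 uses type of therapy as an example of a U&CT subtype, so type may not separate I-ACQUIRE from U&CT. Section 8.3.3.2 has parents agreeing not to change U&CT during the study period, which leaves room for a window longer than four weeks. The 1 to 3 hour range comes from earlier studies and not from this trial's control arm.

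This stands as a limit on the size: 99.7% is conditional. It does not rescue the model, because no variant in the working makes the slope the U&CT effect. Coding Moderate and High as separate types would remove the 60 v 120 contrast, but it would also restore the group indicator that the sentence removes.

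The sentence could instead mean a check on the trial result with hours received in place of assigned group. Over four weeks that model extrapolates, since 4 to 12 h does not overlap 60 to 120 h.

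A reader might go further than the document allows in three ways:
- **That replacing arm costs the trial its randomised comparison.** The primary hypotheses in 9.4.1 and 9.4.2 are still tested between randomised groups. Any analysis of dose received is observational, including the remedy below.
- **That the protocol will report the I-ACQUIRE dose effect as the U&CT effect.** It does not say how the slope will be presented.
- **That a better model would reveal a real dependence.** At this precision, only a very steep one would be detected reliably.

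**Conclusion.** The point holds for the model as stated: a common hours slope does not estimate the impact of U&CT dose. Under a four-week window with type separating the therapies, U&CT supplies about 0.3% of the within-type variation in hours, and opposite truths about U&CT dose move the fitted slope by about 0.001 against an SE of 0.0056. If type does not separate them, the slope is equally blind. Over an assumed 30 weeks the 60 v 120 hour contrast still dominates, at about 67% to 91%, and the slope is a blend.

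These figures rest on uniform U&CT hours, full I-ACQUIRE compliance and the 15/40/70% planning rates. The matter is minor: no primary or secondary test, and no part of the sample size, depends on this model.

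**What to change.** Replace the closing sentence on U&CT dose in 9.4.2, or settle it in the SAP, as follows:
1. Keep randomised arm in the primary logistic model. Add centred U&CT hours (set to 0 in the I-ACQUIRE arms) and U&CT type as terms within the U&CT arm. An hours-by-type interaction, with type separating I-ACQUIRE from U&CT, serves the same end.
2. Define the window over which hours are counted.
3. Report the U&CT hours effect, and the I-ACQUIRE v U&CT contrasts at low, mean and high U&CT hours, with confidence intervals and labelled observational.
4. State in advance that precision is low, so that the result is read as an interval and not as a test.

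The cost is a few lines of text and the added U&CT terms, using U&CT data already documented weekly. The drawback is the width of the interval: over four weeks, roughly ±0.27 log-odds per hour (1.96 x 0.136) if the true slope is zero.
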